## 8.7 Image Analyses

Image acquisition, processing, analysis, and format of reporting will follow standardised procedures that are defined in separate documents (Clinical Imaging Manual, Image Review Charter).

Primary image analysis (e.g. determination of target lesion dimensions of individual time points), as well as secondary image analysis (e.g. RECIST 1.1 classification, considering earlier reference time points) will be performed by a central ICL whose readers are blind to the treatment group.

Reading of morphological imaging (MRI/CT) for determination of progression-free survival (PFS, primary endpoint) will be in duplicate, with adjudication in case of discordance.

All secondary image analyses will be made by a single reader at the central ICL, only.

Results of image analysis will be transferred in a suitable alphanumeric format to the Study Data Management in batches.

## **8.8 Appropriateness of Procedures / Measurements**

The purpose of this study is the evaluation of efficacy and safety of  $^{177}\text{Lu}$ -edotreotide in the treatment of inoperable, progressive, somatostatin receptor-positive GEP-NET in comparison to everolimus, the only medication currently licensed in the target indication advanced low- and intermediate-grade NET of pancreatic or gastroenteric origin. Comprehensive characterisation of survival endpoints (progression-free survival and overall survival), taking into consideration objective response (RECIST 1.1), biomarker response (tumour markers), and symptomatic response (HRQL questionnaires), corresponds to current standards in oncological efficacy evaluation.

Standard safety evaluations (laboratory, ECG) as well as treatment-specific evaluations ( $^{99\text{m}}\text{Tc}$ -MAG3 renal scintigraphy) are included.

Serial planar scintigraphic imaging (2D) is considered the traditional standard method for the evaluation of radiation dosimetry, expected by regulatory agencies. Hybrid dosimetry (2D/3D), based on serial planar and single time point SPECT/CT imaging, is the emerging clinical standard, allowing to investigate absorbed doses to kidneys (safety) and tumour (efficacy) more accurately, due to a higher spatial resolution and more precise delineation of organ-bound activity, compared to 2D dosimetry (see Section [8.2.2](#)).

This approach is considered to be adequate for verifying the therapeutic index of  $^{177}\text{Lu}$ -edotreotide PRRT in greater detail.

## **9 Statistical Methods and Determination of Sample Size**

### **9.1 Randomisation**

Randomisation will be stratified using four independent randomisation lists to control for primary tumour origin (GE-NET vs. P-NET) and for prior medical therapy (1st line vs. 2nd line) as critical baseline co-variables (see Section [9.2.3](#)). A central web-based randomisation system will be used.

## **9.2 List of Variables and Population Characteristics**

For the main analyses of variables based on tumour response, centrally assessed RECIST 1.1 will be used. Local RECIST 1.1 assessment can be used for sensitivity analyses, if deemed relevant.

### **9.2.1 Primary Variable**

#### Progression-free survival

Progression-free survival will be determined starting from randomisation until the date of an event (PD by RECIST 1.1 or death). For the primary analysis, any withdrawal (or drop-out) before EOS visit will be censored. Patients who have not shown progression at the end of the study will also be censored.

### **9.2.2 Secondary Variable(s)**

#### **9.2.2.1 Key Secondary Variables**

- a) Objective response rate (ORR), defined as the percentage of patients, achieving (based on RECIST 1.1) a partial response (PR) or complete response (CR) as best outcome
- b) Overall survival (OS), will be calculated starting from the date of randomisation until the date of death. OS will be determined based on all available evidence, including study visits, follow-up telephone calls, subsequent medical reports, or the report of death, as appropriate. OS will be followed up for 5 years (60 months) after EOS.

#### **9.2.2.2 Exploratory Efficacy Variables**

- c) Percentage of patients progression-free at 2 years after randomisation in either treatment arm (% 2y-PFS)
- d) Disease control rate (DCR), considers – in contrast to the ORR – the percentage of patients, achieving partial response (PR), complete response (CR), and stable disease (SD) as best outcome
- e) Duration of disease control (DDC), will be calculated only in patients who achieve CR, PR or SD as the period from the time point of first establishment of SD (or better) until a new diagnosis of morphological progression per RECIST 1.1 criteria
- f) Similarly, duration of response (DoR), will be calculated only in patients who achieve CR or PR as the period from the time point of first establishment of PR (or better) until a new diagnosis of morphological progression per RECIST 1.1 criteria
- g) Association between RECIST 1.1 tumour response and CgA and/or specific hormone levels will be explored. If relevant, percentage of patients experiencing a biomarker tumour response (CgA, specific hormones), classified as SD, PR, CR, and PD, can be investigated, as well as the duration of such response

**9.2.2.3 Safety and Tolerability Parameters**

- a) Measured tubular extraction rate (TER), percentage depart from baseline value
- b) Calculated glomerular filtration rate (GFR), percentage depart from baseline value
- c) Renal volume ( $V_{\text{kidney}}$ ), percentage depart from baseline value
- d) Frequency of occurrence and severity of abnormal findings in safety investigations (vital signs, 12-lead ECG, clinical laboratory, adverse events)

**9.2.2.4 Health-Related Quality of Life (HRQL)**

- a) Maximum HRQL improvement (EORTC QLQ-C30 and GI.NET21 questionnaires) total scores, relative to baseline
- b) Duration of maximum HRQL improvement
- c) Time to HRQL deterioration, defined as the time from randomisation to first HRQL deterioration

**9.2.2.5 Dosimetry**

Full dosimetry assessments of target organs and tumour lesions will be reported including time to activity curves.

Cumulative absorbed dose (in Gy) of  $^{177}\text{Lu}$ -edotreotide to target tumour lesions and kidneys, will be estimated from dosimetry after first  $^{177}\text{Lu}$ -edotreotide cycle (D1) considering prospective total  $^{177}\text{Lu}$ -edotreotide dose prescriptions from D1 – D4 (assuming dose linearity).

In Sub-study A patients, the cumulative absorbed dose to kidneys and to tumour lesions extrapolated from absorbed dose estimated at D1 will be compared with the cumulative absorbed dose measured at the different administration times (i.e. D1 to D4).

In Sub-study B patients, absorbed dose (in Gy) determined by 3D dosimetry, will be analysed in comparison to absorbed dose values obtained by planar (2D) and hybrid (2D/3D) dosimetry.

In Sub-study C patients, bone marrow absorbed dose (in Gy) will be extrapolated from blood radioactivity.

**9.2.2.6 Pharmacokinetics (Sub-Study C)**

- a) Urine radioactivity in percentage of injected activity (%IA) at pre-defined intervals within 48 hours post-injection to assess excretion pattern
- b) Blood radioactivity in %IA at pre-defined time points within 7 days post-injection to assess clearance pattern
- c) Radiochemical purity assessed through HPLC of urine samples collected within 48 hours post-injection

### **9.2.3 Population Characteristics**

#### **9.2.3.1 Primary Tumour Origin (GE-NET vs. P-NET)**

In this trial patients with histologically confirmed diagnosis of well-differentiated neuro-endocrine tumour of non-functional gastroenteric origin (GE-NET) or both functional or non-functional pancreatic origin (P-NET) will be eligible. Therefore, stratified randomisation will be used to ensure a balanced frequency of GE-NET and P-NET patients in both treatment arms. To enable an optimal subgroup analysis, ideally equal numbers of GE-NET and P-NET should be recruited.

#### **9.2.3.2 Prior Medical Treatment (1st line vs. 2nd line)**

In the present trial both, treatment-naïve (1st line), and patients who have progressed under prior medical therapy (2nd line) will be eligible. Since prior medical treatment status is expected to be a relevant baseline co-variate, stratified randomisation will be used, to ensure a balanced frequency of 1st line and 2nd line subjects in both treatment arms.

In addition, the evaluation of prior medical treatment in patients receiving second line therapy will be differentiated into chemotherapy, SSA, targeted therapy (e.g. sunitinib), and others.

#### **9.2.3.3 Tumour Grade (G1 vs. G2), Ki-67, and KPS**

Tumour grade, Ki-67, and baseline clinical status, determined using the Karnofsky Performance Score (KPS) are suspected to be further relevant baseline co-variables, which should be investigated at the time of analysis.

#### **9.2.3.4 Other Characteristics**

Summary tables and/or listings will be provided for demographics and other baseline characteristics, including:

- Age, ethnic origin, sex, physical exam
- Medical/surgical history at baseline,
- Prior and concomitant medication
- Time from primary diagnosis, time from diagnosis of progression, number and type of prior therapies for condition, site(s) of metastases
- Histological entity, functional state

All variables of population characteristics will be confirmed by non-parametric statistical testing for both treatment groups to check their comparability at baseline (except for detailed physical examination, medications, and medical/surgical history). If there should be major differences between the treatment groups, their impact on analysis will be investigated including with stratified methods, if deemed appropriate.

In addition, appropriate methods (stratification, multivariate analyses, subgroup analyses) will be used to assess the impact of patient and tumour characteristics and tumour histology on tumour response as foreseen in the exploratory study objectives.

## **9.3 Statistical and Analytical Plans**

### **9.3.1 General Considerations**

The primary objective of this trial is to demonstrate the efficacy of PRRT with Lu-edotreotide to prolong progression-free survival (PFS) in patients with inoperable, progressive, SSTR+ GEP-NET, compared to everolimus.

The primary variable progression-free survival (PFS) will be analysed using confirmatory statistics. All survival data will be analysed using the Kaplan-Meier method, which takes into account the impact of censored observations and the Log-rank test. Likewise, the secondary variable overall survival (OS) and PFS, adjusted for the co-variables primary tumour origin, prior medical treatment, tumour grade and baseline KPS, will be compared using exploratory statistics. Further statistical stratified tests will not be made. Instead, the influence of other baseline and/or intercurrent factors such as, but not limited to, concomitant SSA treatment and treatment switch will be investigated by sensitivity analyses.

The main analysis of OS may take into consideration treatment switches if a high proportion (e.g. >33%) of patients in the everolimus arm received subsequent PRRT treatment.

All secondary variables will be analysed descriptively by treatment group. All continuous and ordinal parameters will be summarised using standard summary statistics as appropriate (n, mean, standard deviation, median, minimum, maximum, 25th percentile, and 75th percentile). Summary statistics for ordinal and categorical variables will include frequency counts and percentages. 95% confidence interval will be calculated where relevant. Non-parametric methods will be used for comparison between study groups or subgroups (Mann-Whitney U test), changes within groups (Wilcoxon test) or percentages (Fisher's exact test or Chi test). The influence of censored data will be evaluated by using Kaplan-Meier, log-rank test and Cox model analysis when appropriate.

A statistical power of at least  $P = 0.8$ , and a significance level of  $p < 0.05$  (two-sided) are envisaged. All data will be listed and summarised.

Adverse events prior to the first treatment will be captured for all enrolled patients and reported separately from treatment emergent AEs, as baseline findings.

Patient assignment to the analysis sets, specified in Section 9.3.3, will be performed and listed prior to any analysis taking place.

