In case of unequivocal non-proportional hazards (e.g. crossing survival curves), the main time-to-event analysis can be rather based on Restricted Mean Survival Time (RMST) approach in addition to Log-rank and Cox model. Alternatively, this approach can be used as sensitivity analysis to further investigate the results patterns where deemed appropriate.

The unstratified RMST analysis will be used if there is at least one strata with either:

- 1) too few participants to comparatively analyse;
- 2) no participant followed up for long enough to make a proper comparison

Continuous parameters:

Will be summarized using standard summary statistics as appropriate (n, mean, standard deviation, minimum, 25th percentile, median, 75th percentile and maximum). Corresponding 95% CIs may be presented where meaningful.

Ordinal and categorical variables:

Summary statistics will include

- frequency counts and percentages.
- corresponding 95% confidence interval may be presented where meaningful.

Non-parametric methods will be used for comparison between study groups or subgroups (Mann-Whitney U test), changes within groups (Wilcoxon test) or percentages (Chi² test/Fisher's exact test).

Statistical tests will be stratified for the main analyses (e.g. stratified log-rank test for time to event comparisons, Mantel Haenszel test for percentage comparisons) but appropriate corresponding non-stratified tests can be used where deemed necessary for sensitivity analysis purposes.

[figure not shown]
Other variables will be analysed descriptively or by means of frequency tables.

All data of the clinical database will be listed, summaries will be provided for at least the primary and secondary efficacy endpoints and for the safety endpoints.

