6.7 Impact of COVID Infection

In general, any missing visit/assessment window due to COVID will be documented as protocol deviations. Once a subject misses a visit, the subject's impact on the study conduct will be assessed to help distinguish between data "affected" and "unaffected" by COVID. Specific reasons for COVID-related protocol deviations should be provided as detail as possible, including, but not limited to, confirmed/suspected COVID-19 infection, movement restricted due to COVID or social distancing guidelines, drugs shipping delayed/blocked due to COVID, sponsor/site action due to COVID. A listing will be provided to present the COVID-related protocol deviations.

7 Efficacy Analyses

Parameters	Method	Details
Continuous	Summary statistics	number of observations (N), number of missing observations (Nmiss), mean, standard deviation, minimum, 25th percentile, median, 75th percentile, maximum, lower bound 95% confidence interval, upper bound 95% confidence interval
Ordinal and categorical	Frequency counts and percentages	95% confidence interval
Comparison between groups	Van Elteren test (stratified main analysis) and Wilcoxon test (non-stratified sensitivity analysis)	rank-sum
Changes within groups	Wilcoxon test	signed rank
Comparison of percentages	Mantel Haenszel (stratified main analysis) and Fisher's exact test (non-stratified sensitivity analysis)	contingency table

ITM-LET-01	Statistical Analysis Plan
-------------------	----------------------------------

Influence of censored data	Kaplan-Meier analysis and log-rank test (stratified for main analysis and non-stratified for sensitivity analysis)	as appropriate
	Cox proportional hazard regression	for hazard ratio (HR) computation and when adjusting for covariates
	RMST	in case of unequivocal non-proportional hazards or as sensitivity analysis where deemed appropriate
	treating treatment as time-dependent variable and/or RPSFT and/or censoring at time of switch	to account for new anti-cancer treatment starts and treatment switches in the two arms where necessary

All p-values less than 0.05 will be considered “statistically significant” on a descriptive level. p-values resulting from a main confirmatory test for primary and key secondary endpoints will be considered "statistically significant" according to the interim analysis and multiple testing plan (see Section 5.7).

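### Exploratory continuous outcomes: the general methods list significance tests of change within each arm, and no between-arm analysis adjusts for the outcome's own baseline value

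*Protocol*

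**What the plan says.** Protocol 9.3.1 gives one general rule for continuous variables: "Non-parametric methods will be used for comparison between study groups or subgroups (Mann-Whitney U test), changes within groups (Wilcoxon test) or percentages". The same section says "Further statistical stratified tests will not be made".

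SAP 6 repeats the within-group element ("changes within groups (Wilcoxon test) or percentages") but adds "Statistical tests will be stratified for the main analyses". The methods table in SAP 7 has a row headed "Changes within groups" that assigns the Wilcoxon signed-rank test. For comparisons between groups it names the van Elteren test as the stratified main analysis and keeps the unstratified Wilcoxon test for sensitivity. Below the table, SAP 7 adds a labelling rule that begins "All p-values less than 0.05 will be considered": such results are to be called significant, though only descriptively.

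Baseline enters through change from baseline. Protocol 9.2.2.3 defines the renal variables as "percentage depart from baseline value". SAP 8.5 presents relative change by arm and visit with box plots of raw values. SAP 8.4 summarises laboratory values, raw and as change, by visit and arm. SAP 9 gives box plots of HRQL scores, summaries of maximum improvement and proportions changing by at least 10 points. The comparison it names is a stratified log-rank test on time to deterioration, with a Cox hazard ratio. No section specifies ANCOVA, a rank version of it, or a repeated-measures model for a continuous outcome.

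**The concern.** The randomised question is whether the arms differ. A signed-rank test inside one arm asks whether that arm moved from baseline, and its power grows with the number of patients in the arm. With 2:1 allocation, the same true change is more likely to reach p<0.05 under PRRT than under everolimus. A reader shown two within-arm p-values may take that as a treatment difference. The misreading could flatter PRRT (a significant HRQL gain in one arm only) or count against it (a significant fall in renal function in one arm only).

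The second issue is precision. The baseline value is collected, but it is used only by subtraction or as a percentage. Using it as a covariate gives a tighter between-arm estimate. A rank test on its own also gives no estimate of the size of the difference.

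**Working it through.** **Figures in the plan.** The documents give no effect size, SD, correlation or power for any continuous outcome, so there is no stated figure to reproduce. The inputs taken from them are 200 versus 100 patients (Protocol 3.1, SAP 3.1), two-sided 5% tests for exploratory variables (Protocol 9.3.4, SAP 5.3 and 5.7) and 15% dropout (SAP 4, stated for PFS and used here only as an illustration). The rest is assumed: true standardised change d of 0.10 to 0.40, baseline correlation ρ of 0.3 to 0.7, and normal data without ties.

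**Step 1: power of the within-arm test.** The normal approximation for the signed-rank test is Φ(d·√(3n/π) − 1.96). At d = 0.20:
- n = 200: 0.20 × √190.99 = 2.764; Φ(0.804) = 0.79
- n = 100: 0.20 × √95.49 = 1.954; Φ(−0.006) = 0.50

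The arms are independent, so PRRT only is significant with probability 0.79 × 0.50 ≈ 0.40, and everolimus only with 0.50 × 0.21 ≈ 0.10.

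**Step 2: simulation, 20,000 trials, identical true change in both arms, 200 versus 100.**

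| d (SD of change) | Power PRRT | Power everolimus | PRRT only | Everolimus only |
|---|---|---|---|---|
| 0.10 | 28.5% | 15.9% | 23.9% | 11.4% |
| 0.15 | 54.8% | 30.0% | 38.5% | 13.7% |
| 0.20 | 78.4% | 49.0% | 40.2% | 10.7% |
| 0.25 | 93.0% | 68.2% | 29.5% | 4.7% |
| 0.30 | 98.5% | 82.5% | 17.3% | 1.3% |
| 0.40 | 100% | 97.2% | 2.8% | 0.0% |

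In the same data a direct Mann-Whitney comparison of the arms rejects in 4.7 to 5.0% of trials, as it should.

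**Step 3: other arm sizes.**
- 170 versus 85 (15% dropout): PRRT only 41% and everolimus only 12% at d = 0.20; 35% and 7% at d = 0.25.
- 100 versus 50 (attrition as patients progress): PRRT only peaks at about 42%, at d = 0.25.
- 150 versus 150, d = 0.20: 23% and 22%. Discordance is as likely in either direction.

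The 2:1 ratio therefore tilts discordant results towards PRRT. It does not create them.

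**Step 4: precision.** With unit variance at each time point, a change score has variance 2(1 − ρ) and ANCOVA has 1 − ρ². The ratio is (1 + ρ)/2, which is 0.65, 0.75 and 0.85 at ρ = 0.3, 0.5 and 0.7, so ANCOVA variance is 35%, 25% and 15% lower. To express this as power, take a difference of 0.343 SD. An analysis of the raw follow-up value has 80% power there: (1.96 + 0.84) × √(1/100 + 1/200) = 0.343. At the same three correlations a change score has 66%, 80% and 95% power, and ANCOVA about 83%, 90% and 98%.

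**The case against.** The strongest reply is that little in the plan depends on this. Protocol 9.3.4 leaves detailed procedures and changes of method to the SAP, and SAP 7 makes a stratified test the main between-arm analysis. The signed-rank test appears only in generic method lists. The endpoints in SAP 7.1 to 7.3 are times to event or proportions, plus biomarkers handled descriptively, and none is assigned a within-arm test. Nor are laboratory values, renal measures or HRQL scores in SAP 8.4, 8.5 and 9. Tests outside PFS, ORR and OS are exploratory. Rank methods are a reasonable choice for bounded or skewed data.

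All of this stands, and it rules out several stronger readings that a reader might infer:
- **That the arms are compared only by an unadjusted Mann-Whitney test.** That is the protocol's wording. The SAP's main test is stratified, although it does not adjust for the outcome's own baseline value.
- **That the plan commits to reporting a significant change for PRRT and none for everolimus.** No named variable is assigned the within-arm test, and a valid between-arm rank test is listed beside it.
- **That baseline is ignored.** Change and percentage change both use it, so the covariate's gain is incremental and shrinks as the correlation rises.
- **That the HRQL comparison loses this much power.** The named HRQL comparison is a log-rank test, to which the ANCOVA figures do not apply.

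The reply does not remove the within-group test from three method lists, or the labelling rule that would apply to it. It also does not supply a between-arm estimate where the specific sections give none. A descriptive label does not turn a within-arm p-value into a comparison.

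**Conclusion.** The point holds as an inexpensive improvement to the exploratory analyses. Both documents list within-arm tests, and neither specifies a baseline-adjusted between-arm analysis for a continuous outcome. If within-arm p-values are reported side by side at 200 versus 100, an identical change of 0.15 to 0.25 SD appears significant for PRRT only in about 30 to 40% of trials and for everolimus only in about 5 to 14%. The PRRT-only figure is 17% at 0.30 SD and 3% at 0.40 SD, so the problem is confined to small true changes.

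The size rests on assumed changes and normal data, and the precision gain on assumed correlations; the documents supply none of these. A reader might infer that the trial's conclusions are at risk. They are not: PFS, ORR and OS are the only confirmatory endpoints, and none is continuous.

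The two documents also differ on stratified testing. Protocol 9.3.1 rules out further stratified tests, while SAP 6 and 7 make them the main analysis.

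**What to change.** - In Protocol 9.3.1 and SAP 6 and 7, delete the within-group Wilcoxon tests. Descriptive change by arm can stay, without p-values.
- For each continuous variable that is to be compared, report the between-arm difference by visit with a 95% CI from ANCOVA or a repeated-measures model (on ranks if skewed). Use the baseline value and the two randomisation factors, tumour origin and line of therapy, as covariates.
- Keep the van Elteren test on the change score as a sensitivity analysis.
- Cross-refer to this analysis from SAP 8.4, 8.5 and 9 for the variables it covers. State how patients without a baseline value are handled; SAP 9 already anticipates some for HRQL.
- Reconcile the Protocol 9.3.1 sentence on stratified tests with SAP 6 and 7.

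The cost is SAP and protocol wording and modest reprogramming. No new data are needed, and nothing changes for PFS, ORR or OS.
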